5.3 Removal of Subjects from Treatment

The participation of a subject in the study or the administration of treatment may be terminated at any time for one of the following reasons:

- The subject desires to discontinue study treatment.
- The subject withdraws consent to participate in the study.
- The subject is unwilling or unable to comply with the safety procedures.
- The subject is discovered to be pregnant.
- The subject experiences a medical emergency that necessitates withdrawal.
- The subject is withdrawn at the discretion of the Investigator for medical reasons or non-compliance.

Confidential Page 20 of 42

- AST or ALT $> 8 \times ULN$
- ALT or AST > 3 x ULN AND total bilirubin > 2X ULN
- AST or ALT > 3 x ULN AND patient has right upper quadrant pain or eosinophilia
- Hypersensitivity
- Shock or anaphylactoid symptoms
- Absolute neutrophil count <800 cells/mm³
- Hemoglobin <11 g/dL for women and <12 g/dL for men
- Serum creatinine concentration ≥1.5× ULN
- Confirmed creatinine clearance (CrCl) < 50 mL/min by Cockcroft-Gault
- Platelet count <75,000 cell/mm³.
- Hepatic function disorder or jaundice (both incidences unknown).
- Hyperkalemia (incidence unknown). Severe hyperkalemia may occur.

A subject whose treatment is terminated should remain in the study for appropriate follow up assessments whenever possible.

6 STUDY TREATMENT - CAMOSTAT MESILATE

6.1 Study Drug

Camostat will be supplied as 100mg unprinted tablets to be stored at controlled room temperature (15°C to 30°C [59°F to 86°F]). One Pharmaceuticals has prepared matched placebo tablets, which they will also supply to us along with camostat tablets. Matching placebo will be provided in tablet form to be stored at controlled room temperature (15°C to 30°C [59°F to 86°F]).

Standard Dose

Subjects randomized to the camostat mesilate + SOC arm will be administered. Day 1 is deemed to be the first 24 hours after enrollment into the study, with time 0 (time of first dose) occurring as soon as possible after the subject's eligibility has been confirmed.

Subjects randomized to the SOC + placebo arm will be administered. Day 1 is deemed to be the first 24 hours after enrollment into the study, with time 0 (time of first dose) occurring as soon as possible after the subject's eligibility has been confirmed.

6.2 Administration of Camostat mesilate or placebo

The tablets will be dispensed in appropriately sized amber prescription containers with child-resistant caps. The prescription container and caps are manufactured from PP (polypropylene plastic).

Camostat mesilate is provided as 100 mg tablets and dosed orally. Subjects will be instructed to take their doses at least two hours after a meal and one hour before the next meal, and at bedtime.

Subjects who vomit during or immediately after dosing, should not be re-dosed.

6.3 Outpatient Camostat mesilate Dosing

Subjects in the camostat mesilate + SOC arm, will be dispensed sufficient camostat mesilate to ensure continued dosing until their next study visit.

Confidential Page 21 of 42

Subjects will also be instructed that if they miss a dose, they should follow the guidelines:

- 1) If more than 1/2 the time until their next dose has elapsed, they SHOULD NOT take the dose. They should just take the next dose at the normal scheduled time.
- 2) If less than 1/2 the time until their next dose has elapsed, they should take the missed dose immediately.
- 3) In both cases, they should then return to their regular dosing schedule.

6.4 Drug Accountability

The Investigator must maintain adequate records showing the receipt, dispensation, or other disposition of camostat mesilate including the date, quantity and identification of subjects (study ID) who received camostat mesilate. Drug supplies will be inventoried and accounted. Unused supplies of all camostat mesilate will be returned to the Sponsor or destroyed on site in accordance with local procedures upon approval of the Sponsor.

6.5 Treatment Compliance

The pharmacy will provide bottles of camostat mesilate for outpatient use (Exact dispensing instructions for outpatients will be described in the pharmacy instructions). Assessment for compliance with each dose will be monitored and recorded in accordance with site standard operating procedures.

6.6 Treatment Precautions

An overdose is defined as any dose of study drug given to a subject or taken by a subject that exceeds the dose described in this document. In the event of an overdose, the subject's symptoms should be treated, and the Sponsor informed.

6.7 Clinically Significant Adverse Reactions

As indicated on the FOIPAN label (Japanese approved product), the below listed clinically significant adverse reactions may occur. Patients should be carefully monitored. If any abnormalities are observed, appropriate measures such as discontinuing the administration should be taken.

- Shock or anaphylactoid symptoms (both incidences unknown). If any symptoms such as decreased blood pressure, dyspnea, and pruritus are observed, administration should be discontinued and appropriate measures be taken.
- Thrombocytopenia (incidence unknown).
- Hepatic function disorder or jaundice (both incidences unknown).
- Hepatic function disorder accompanied by remarkable increase of AST (GOT), ALT (GPT), γ-GTP, Al-P, or jaundice may occur.
- Hyperkalemia (incidence unknown). Severe hyperkalemia may occur.

6.8 Other Adverse Reactions

Confidential Page 22 of 42

| Incidence ¹ /Adverse Reaction | 0.1%-0.5% | <0.1% | Unknown |
|---|--|--|--------------|
| Hematologic | | Leukopenia, erythrocytopenia | Eosinophilia |
| Hypersensitivity ² | Rash, pruritus | | |
| Gastrointestinal | Nausea, abdominal discomfort, abdominal fullness, diarrhea | Anorexia, vomiting, dry mouth, heartburn, abdominal pain, constipation | |
| Hepatic | Increased AST (GOT), ALT (GPT), etc. | | |
| Renal | | Increased BUN, increased creatinine | |
| Other | | Edema, hypoglycemia | |

¹ The incidences are calculated by including reports from the drug use surveillance

6.9 Prohibited Concomitant Therapy

The following may interact with camostat mesilate and risks and benefits should be carefully considered prior to treatment with the following:

• Any other anti-viral medication whether investigational or approved.

7 STUDY PROCEDURES

Refer also to Section 14: Schedule of Assessments

7.1 Day 1 (PRE-DOSE)

- Obtain informed consent.
- Verify eligibility per the inclusion and exclusion criteria. (See Sections 5.1 and 5.2)
 - o Review and record medical history to ensure there are no exclusionary illnesses.
 - Review and record concomitant medications for possible prohibited medications. (See Section 6.7)
 - Record date of onset of symptoms
- If subject is female of child-bearing potential and meets inclusion criteria 5.e, obtain urine pregnancy test and proceed if result is negative.
- Measure and record vital signs (BP, HR, Temp, Resp).

Confidential Page 23 of 42

² If such symptoms are observed, administration should be discontinued.

- Collect and record SPO2 by Finger Sensor
- Perform Physical exam (may be done by the Principal Investigator or their designee)
- Collect oropharyngeal swab for virologic testing by RT-PCR and resistance testing.
- Collect blood samples for:
 - o Antibodies to SARS-CoV-2.
 - o Hematology and clinical chemistry laboratory analyses
 - Biobanking
- Perform subject randomization (via EDC) to establish treatment arm (camostat mesilate + SOC or SOC + placebo).
- Explain in home procedures for the study (self-sampling of nasal swabs, temperature, SPO2, completing the daily questionnaire).
- Provide supplies to research subject and review the calendar of return visits

7.2 Day 1 (FIRST DOSE AND POST-DOSE)

NOTE: Day 1 is deemed to be the first 24 hours after enrollment into the study, with time 0 (time of first dose) occurring as quickly as possible after the subject's eligibility has been confirmed.

- Administer first dose (200 mg camostat mesilate or placebo) at time 0.
- Monitor patient for 30 minutes after their first dose.

7.3 Days 5, 10, 28 (Follow-up) or Early Termination

- Conduct and record the results of a Physical Exam.
- Review and record concomitant medications (Note: if there have been changes in concomitant medications during the study, determine whether the change is due to an AE).
- Measure and record vital signs (BP, HR, Temp, Resp).
- Collect and record SPO2 by Finger Sensor
- Collect blood samples for:
 - o Antibodies to SARS-CoV-2. (28)
 - o Biobanking (Day 10 and Day 28)
 - o Hematology and clinical chemistry laboratory analyses (Day 5, 10, 28)
 - o Drug level one hour after dosing (Day 5)
- Assess and record clinical status according to the following study-specific 7-point scale:
 - 1. Not hospitalized
 - 2. Hospitalized, not requiring hospital care due to lack of housing
 - 3. Hospitalized, not requiring supplemental oxygen
 - 4. Hospitalized, requiring supplemental oxygen
 - 5. Hospitalized, on non-invasive ventilation or high flow oxygen devices
 - 6. Hospitalized, on invasive mechanical ventilation or ECMO

Confidential Page 24 of 42

- 7. Death
- Collect oropharyngeal swab for virologic testing (RT-PCR) and resistance analysis.
- Collect and record adverse events (see Section 8.3 for detailed instructions).

8 EFFICACY, PHARMACOKINETICS AND SAFETY ASSESSMENTS

8.1 Efficacy Assessments

Primary Measurement (Efficacy):

1. Nasal swab for PCR taken daily from Day 1 to Day 10, and Days 14, 21, and 28.

Secondary Measurements (Efficacy):

- 1. Symptom improvement or worsening: Subjects will fill in a diary daily (see Appendix A2), recording the following symptoms:
 - a. Cough
 - b. Sore throat
 - c. Headache
 - d. Nasal congestion
 - e. Body aches and pains
 - f. Fatigue
 - g. Oral temperature taken at a consistent time each day and at least four hours after ingesting the most recent antipyretic (acetaminophen or NSAID)
 - h. Dyspnea
 - i. Shaking chills
 - i. Loss of taste
 - k. Loss of smell
 - 1. GI symptoms including nausea, vomiting, and/or diarrhea
 - m. Chest pain
- 2. Blood for determination of antibodies to SARS-CoV-2 will be obtained on Days 1 and 28.
- 3. Number of subject hospitalizations, emergency department visits, incidence of respiratory failure, deaths, and proportions of subjects alive, not hospitalized, and free of respiratory failure on day 28

8.2 Required Resistance Testing

Resistance testing, as required in clinical trials of anti-viral drugs will be performed at each time point that oropharyngeal swabs are taken.

8.3 Safety Assessments

Abnormal clinical laboratory values that are clinically significant and all reported adverse events will be graded according to the Common Terminology Criteria for Adverse Events (CTCAE) version 5.0.

Safety will be assessed by the collection of observed and reported adverse events, physical exams, vital signs and the following clinical laboratory tests:

Hematology

Confidential Page 25 of 42

Hemoglobin (Hgb)

Platelet count

Red blood cell count

White blood cell count with differential

Chemistry

Blood Urea Nitrogen (BUN) Creatinine

Total bilirubin Alkaline Phosphatase

Aspartate transaminase (AST) Alanine transaminase (ALT)

Lactic dehydrogenase (LDH)

Glucose Albumin
Total protein Bicarbonate

Sodium

Potassium Chloride

Calcium

Urate C-reactive protein

NOTES:

• All clinical laboratory assessments listed above (hematology and chemistry) will be conducted at the Stanford University Medical Center clinical laboratory.

• If coagulation assays are ordered as part of the SOC, the results should be added to the EDC.

Including Clinical Laboratory Testing, subjects will undergo four planned venipunctures during this study.

8.3.1 Adverse Events

Treatment-emergent AEs will be defined as those occurring coincident with start of treatment through 28 days post-treatment.

Subjects will be instructed to report AEs during the study and staff will query subjects regarding AEs throughout the study. The Investigator (and/or designee) must document all AEs reported through completion of the Day 28 visit. Any subject who is withdrawn from the study due to an AE shall be followed until the event has resolved or stabilized or, if in the camostat mesilate arm, 14 days after last dose. The Investigator will document available follow-up information on the subject's source documentation and CRF

8.3.2 Definition of an Adverse Event

The FDA Safety Guidance, referencing 21CFR312.32(a), defines an Adverse Event as follows:

Adverse event means any untoward medical occurrence associated with the use of a drug in humans, whether or not considered drug related.

An adverse event (also referred to as an adverse experience) can be any unfavorable and unintended sign (e.g., an abnormal laboratory finding), symptom, or disease temporally associated with the use of a drug and does not imply any judgment about causality. An adverse event can arise with any use of the drug (e.g., off-label use, use in combination with another drug) and with any route of administration, formulation, or dose, including an overdose.

Confidential Page 26 of 42

Adverse Events are **NOT**:

- Clinical events related to the progression of COVID-19.
- Medical or surgical procedures (e.g., surgery, endoscopy, tooth extraction, transfusion). The condition that leads to the procedure is the AE.
- Situations where an untoward medical occurrence has not occurred (e.g., hospitalization for elective surgery, social and/or convenience admissions).

8.3.3 Evaluating and Reporting of Adverse Events

All AEs (i.e. a new event or an exacerbation of a pre-existing condition) that occur after dosing with camostat mesilate and after completion of baseline assessments in the SOC + placebo arm, must be recorded as an AE or SAE (if applicable), on the Adverse Event eCRF and SAE form, as applicable. The Investigator must follow all AEs until the AE resolves, or until the Investigator and/or the Medical Monitor determine the event is chronic or clinically stable. If an AE remains unresolved at the conclusion of the study, the Investigator and Medical Monitor will make a clinical assessment to determine whether continued follow-up of the AE is warranted. All subjects who have received at least one exposure to study therapy will be evaluated for safety of study treatment.

The Investigator should attempt to establish a diagnosis of the event based on signs, symptoms and/or other clinical information. In such cases, the diagnosis should be documented as the AE and not the individual signs/symptoms.

All AEs must be promptly documented on the Adverse Event eCRF and assessed by the Investigator. Details of the event must include the dates of onset and resolution, severity, relationship to study drug, seriousness, and whether the event caused the subject to withdraw from the study, outcome and timing with regard to administration of the study drug. We will categorize the AES using the Division of AIDS Table for Grading the Severity of Adult and Pediatric Adverse Events.

Severity: Severity should be graded and recorded as follows:

- Grade 1 Mild: No or minimal interference with usual activities; intervention not indicated
- Grade 2 Moderate: Greater than minimal interference with usual activity; intervention indicated
- Grade 3 Severe: Inability to carry out usual activity, incapacitating; requires intervention or hospitalization
- Grade 4 Potentially life-threatening: Inability to perform self-care; intervention indicated to prevent permanent impairment, disability or death
- Grade 5 Death

Relationship: The relationship of the Adverse Event to the study drug will be determined by the Principal Investigator, and assessed using the following definitions:

- **Related:** There is a distinct temporal relationship between the event onset and administration of the study drug. There is a known reaction to agent or chemical group or predicted by known pharmacology. The event cannot be explained by subject's clinical state or other factors.
- **Unrelated:** Evidence exists that the AE has an etiology other than the study drug (e.g., pre-existing condition, underlying disease, intercurrent illness, or concomitant medication).

Confidential Page 27 of 42

These criteria, in addition to good clinical judgment, should be used as a guide for determining the causal assessment. If it is felt that the event is not related to study drug therapy, then an alternative explanation should be provided.

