8.3.4 Serious Adverse Events (SAEs)

All SAEs as defined below and that occur after the first dose of camostat mesilate and up to Day 28 must be reported to the Sponsor as soon as the site becomes aware of them. Any SAEs occurring after Day 28 and considered at least possibly drug-related must also be reported.

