8.4 Suspected Unexpected Serious Adverse Reactions (SUSARs)

A SUSAR carries specific and time-based reporting requirements for the Sponsor of a clinical trial. Thus, after an Investigator reports an SAE, the FDA expects the Sponsor will determine whether it meets the definition of a SUSAR.

A SUSAR is defined according to 3 criteria:

- 1. The AE is deemed a "suspected adverse reaction" if there is a reasonable possibility that the study drug caused the AE. A "reasonable possibility" means there is evidence to suggest a causal relationship between the drug and adverse event.
- 2. The AE is "Serious" if it meets the definition of an SAE provided in section 8.3.5
- 3. The AE is deemed "unexpected" if it is not listed in the Investigator's Brochure (IB) or if in the IB, has not been reported at the severity observed.

In cases where the Sponsor deems a SUSAR has occurred, it must file an IND Safety Report with the FDA. Sponsorwill require the assistance and cooperation of the Investigator and staff to provide accurate and complete information on the subject and observed SAE so that reporting requirements to the FDA can be met.

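### The two-level causality scale in 8.3.3 sets a stricter test for Related than 8.4 and 8.3.4 use, and leaves a novel reaction with no category

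*Combined protocol and SAP*

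**What the plan says.** Section 8.3.3 has the principal investigator rate the relationship of each adverse event to study drug, using definitions that it then gives. There are two.

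- *Related* consists of three sentences with no *or* between them. The first asks for a clear link in time between onset and dosing. The second reads "There is a known reaction to agent or chemical group or predicted by known pharmacology". The third rules out other causes, in these words: "The event cannot be explained by subject's clinical state or other factors".
- *Unrelated* begins "Evidence exists that the AE has an etiology other than the study drug", and the underlying disease is among its examples.

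The section adds that the criteria are a guide to be used alongside clinical judgment, and that a rating of not related should come with an alternative explanation.

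Two other sections use a causality standard. In 8.4 an event is a suspected adverse reaction "if there is a reasonable possibility that the study drug caused the AE", which the section explains as evidence suggesting a causal link. In 8.3.4, SAEs after Day 28 that are "considered at least possibly drug-related must also be reported".

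The rating feeds 9.10, which summarises TEAEs by relatedness and gives treatment-related versions of the overall counts, with between-arm differences in proportions.

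**The concern.** The investigator's scale, the sponsor's SUSAR test and the late-SAE trigger should ask the same causal question. They do not. The investigator's test is the strictest, the scale has gaps, and the trial population is one in which the disease can explain many of the drug's own listed effects.

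Three things are at stake. The treatment-related rows of the safety summary may understate what the investigators saw. Whether an SAE after Day 28 is reported depends on a level that no rater is given. And 2.7 says the study should help define the safety profile in this setting, so a reaction not seen before is exactly what the scale must be able to record.

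**Working it through.** No alpha, power or event count enters this point, and the plan gives no figure to reproduce. The check is a comparison of text with a few counts.

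**Step 1. The three standards side by side.**

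| Section | Applied by | Used for | What must be shown |
|---|---|---|---|
| 8.3.3, Related | Investigator | AE record, tables in 9.10 | Distinct timing, known or predicted reaction, no other explanation |
| 8.4 | Sponsor | SUSAR decision | Reasonable possibility of causation |
| 8.3.4 | Site, as reporter | SAEs after Day 28 | At least a possible link |

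With no *or* between them, the natural reading of the three sentences in 8.3.3 is that all must hold. An event can meet either of the other two standards and fail this one.

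**Step 2. Test events put through 8.3.3 as written.**

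- *A novel reaction, well timed, neither known nor predicted, with no evidence of another cause.* It fails the second sentence, so it is not Related. It has no evidence of another cause, so it is not Unrelated. It has no category.
- *A listed reaction that COVID-19 also produces.* It meets the second sentence but fails the third whenever COVID-19 could explain it. Because underlying disease is a named example of another cause, the rating leans toward Unrelated.
- *A reaction predicted by pharmacology but absent from the Investigator's Brochure, or a listed reaction at greater severity.* It can meet the second sentence and still be unexpected under 8.4. Here the two sections do not collide.
- *An SAE after Day 28 with a possible but unproven link.* Section 8.3.4 requires a report, but 8.3.3 offers no such level to select.

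**Step 3. Overlap between drug and disease.** The 0.1%-0.5% column in 6.8 includes rash and, in the gastrointestinal row, "Nausea, abdominal discomfort, abdominal fullness, diarrhea". The column below 0.1% includes vomiting and abdominal pain. Matched against the symptom list in 5.1, the overlap is rash, nausea, diarrhea, vomiting and abdominal pain: 3 + 2 = 5 reactions.

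**Step 4. Reach in 9.10.** The overall TEAE summary has eight categories: any, serious, leading to discontinuation and leading to death, each once for all causes and once for treatment-related events. So 4 of 8 depend on the rating.

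**Step 5. Direction.** Let *a* and *b* be the proportions of camostat and placebo subjects with an event that meets the test in 8.4. Let *s* be the fraction of them also rated Related under 8.3.3, taken as equal in both arms because raters are blinded. The tables would then show *s·a* and *s·b*, and a difference of *s(a − b)*. With *s* anywhere from 0 to 1, both the counts and the absolute difference shrink or stay the same. The documents give no value for *s*, so only the direction can be stated.

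**The case against.** The strongest reply is that 8.3.3 calls its criteria a guide, never says that all three sentences must hold, and asks for an alternative explanation before an event is rated not related. That stands in part. A reader might infer that COVID-like or unexpected reactions can never be called related; the text does not support that. Judgment can override the criteria, and *unexpected* in 8.4 means missing from the Investigator's Brochure or more severe than reported there, which is not the same as unknown and unpredicted. But judgment does not supply a missing category or reconcile three standards. It leaves each rater to resolve the conflict alone.

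A reader might also infer that SUSAR reporting is blocked. It is not. Under 8.3.6, SAEs go to the sponsor within 24 hours whatever their cause, and under 8.4 the sponsor makes the SUSAR decision on its own test. This safeguard stands for SAEs through Day 28. It does not cover the ratings of non-serious events or the reporting of SAEs after Day 28.

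The effect may also be small. Each treatment-related row has an all-cause counterpart, so no recorded event leaves the tables, and the planned Chi-squared or Fisher comparison is of AEs, not of related AEs. At the upper limits in 6.8, the five overlapping reactions would yield about 60 × (3 × 0.5% + 2 × 0.1%) = 60 × 1.7% = 1.02 reports in the camostat arm. Those rates include drug use surveillance and may not carry over to this trial, but the documents give no larger ones.

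Finally, part of the overlap arises earlier. Section 8.3.2 does not count COVID-19 progression as an adverse event, and 9.10 codes AEs other than COVID-19 symptoms. Events removed there never get a rating, and rewording Related will not recover them.

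**Conclusion.** Wrong as written, in a limited way. The definition of Related in 8.3.3 is stricter than the tests in 8.4 and 8.3.4, a novel reaction with no other evident cause has no category, and five listed reactions lean toward Unrelated because the disease shares them. The four treatment-related categories of the eight in 9.10 would tend to undercount, and the late-SAE trigger rests on a level that the scale does not define.

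This assumes that the three sentences are read as cumulative and that raters follow them. The more raters rely on clinical judgment, the smaller the undercount, but the less consistent the ratings. The size of the undercount cannot be estimated from the documents. The primary efficacy analysis and the all-cause safety counts are unaffected. The wording should be corrected, because it governs half of the overall TEAE categories and the correction is already available in the protocol's own text.

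**What to change.** In 8.3.3, define Related as a reasonable possibility that study drug caused the event, with the explanation of that term given in 8.4. Keep the present three sentences only as considerations for the judgment. Define Unrelated as no reasonable possibility, and keep the requirement for an alternative explanation. That requirement matters: without it, Unrelated would become an easy default. In 8.3.4, replace the possibly-related wording with Related as so defined.

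Every event then has a category, and the investigator, the site and the sponsor apply one test. The cost is a few lines of text. The downside is that somewhat more events will be classed as related, in both arms.
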